6.4. Pre-screen/Screen/Run-in Failures

Pre-screen/screen failures/run-in failures are defined as subjects who consent to participate in the clinical trial but are never subsequently randomized. In order to ensure transparent reporting of screen failure subjects, meet the Consolidated Standards of Reporting Trials (CONSORT) publishing requirements, and respond to queries from Regulatory authorities, a minimal set of screen failure information is required including, but not limited to Demography, Screen Failure details, Eligibility Criteria and Serious Adverse Events (see Section 8.4.1.5).

For the purposes of this study pre-screen/screen failures/run-in failures will be defined as follows:

- Subjects will be assigned a study number at the time of signing the informed consent (Pre-screen Visit). Subjects who do not progress to the Screening Visit will be deemed a pre-screen failure.

- Those subjects that complete at least one additional Visit 1 (Screening) procedure but do not enter the run-in period will be designated as screen failures.
- Those subjects that enter Part A or Part B, but are not randomized, will be designated as run-in failures.

Subjects who fail to meet inclusion and exclusion criteria at Visit 1 will be considered screen failures and cannot be re-screened.

6.5. Study Withdrawal Prior to Randomization: Withdrawal during Part A or Part B

Subjects have the right to discontinue study participation before the end of the study. A subject may also be asked to discontinue study participation at the investigator's discretion or because the subject met the protocol defined stopping criteria detailed below.

Subjects in Parts A or B of the study **MUST** discontinue study participation if any of the following stopping criteria are met:

1. **Liver Chemistry:** Meets any of the protocol-defined liver chemistry stopping criteria (see [Appendix 2](#)).

Liver chemistry stopping and increased monitoring criteria have been designed to assure subject safety and evaluate liver event etiology (in alignment with the FDA premarketing clinical liver safety guidance).

<http://www.fda.gov/downloads/Drugs/GuidanceComplianceRegulatoryInformation/Guidances/UCM174090.pdf>

If the liver chemistry stopping criteria are met by any subject participating in this study, treatment restart or re-challenge is not permitted.

2. **Pregnancy:** Positive pregnancy test
3. **Laboratory abnormality:** Evidence of clinically significant abnormality in the haematological or biochemical screen, which in the opinion of the investigator would make the subject unsuitable for participation in this study.
4. **Hepatitis Status:** Positive Hepatitis B Surface Antigen (HBsAg) screen conducted at Visit 1.
5. **ECG:** Discontinuation is required if any of the following ECG criteria are met during the study:
 - QTcF>500 msec or uncorrected QT>600 msec
 - Change from Visit 1 baseline: QTcF> 60msec

For patients with underlying **bundle branch block**, follow the discontinuation criteria listed below:

Visit 1 Baseline QTc with Bundle Branch Block	Discontinuation QTc with Bundle Branch Block
< 450 msec	> 500 msec
450 – 480 msec	≥ 530 msec [Note: QTc(F)>500 msec for Korean subjects]

Details on performing ECG assessments can be found in Section 8.4.5.

Subjects who discontinue open-label mepolizumab/withdraw from study participation during Part A or Part B should return to the clinic for an Early Withdrawal (EW) visit (Section 6.6.1) and to return any study materials approximately 4 weeks following their last dose of open-label mepolizumab. No additional follow-up is needed.

Subjects withdrawing from study participation in Part A or Part B, prior to randomization will be classified as **run-in failures**, as appropriate (Section 6.4).

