13.2. Appendix 2: Liver Chemistry Stopping and Increased Monitoring Algorithm

Phase III-IV Liver Chemistry Stopping and Increased Monitoring Algorithm

Liver Safety Required Actions and Follow up Assessments Section can be found in [Appendix 3](#).

Phase III-IV Liver Chemistry Increased Monitoring Algorithm with Continued Therapy for ALT ≥3xULN but <8xULN

Liver Safety Required Actions and Follow up Assessments Section can be found in [Appendix 3](#).

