13.3. Appendix 3: Liver Safety Required Actions and Follow up Assessments

Phase III-IV liver chemistry stopping and increased monitoring criteria have been designed to assure subject safety and evaluate liver event etiology (in alignment with the FDA premarketing clinical liver safety guidance).

<http://www.fda.gov/downloads/Drugs/GuidanceComplianceRegulatoryInformation/Guidances/UCM174090.pdf>

Phase III-IV liver chemistry stopping criteria and required follow up assessments

Liver Chemistry Stopping Criteria - Liver Stopping Event	
ALT-absolute	ALT \geq 8xULN
ALT Increase	ALT \geq 5xULN but <8xULN persists for \geq 2 weeks ALT \geq 3xULN but <5xULN persists for \geq 4 weeks
Bilirubin^{1,2}	ALT \geq 3xULN and bilirubin \geq 2xULN (>35% direct bilirubin)
INR²	ALT \geq 3xULN and INR>1.5, if INR measured
Cannot Monitor	ALT \geq 5xULN but <8xULN and cannot be monitored weekly for \geq 2 weeks ALT \geq 3xULN but <5xULN and cannot be monitored weekly for \geq 4 weeks
Symptomatic³	ALT \geq 3xULN associated with symptoms (new or worsening) believed to be related to liver injury or hypersensitivity
Required Actions and Follow up Assessments following ANY Liver Stopping Event	
Actions	Follow Up Assessments

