
 Immediately discontinue study treatment Report the event to GSK within 24 hours Complete the liver event CRF and complete an SAE data collection tool if the event also meets the criteria for an SAE² Perform liver event follow up assessments Monitor the subject until liver chemistries resolve, stabilize, or return to within baseline (see MONITORING below) Do not restart/rechallenge subject with study treatment. Restart/rechallenge is not allowed, permanently discontinue study treatment and subject may continue in the study for any protocol specified follow up assessments 	
 Viral hepatitis serology⁴ Only in those with underlying chronic hepatitis B at study entry (identified by positive hepatitis B surface antigen) quantitative hepatitis B DNA and hepatitis delta antibody⁵. Blood sample for pharmacokinetic (PK) analysis, obtained within 4 weeks after last dose⁶ Serum creatine phosphokinase (CPK) and lactate dehydrogenase (LDH). Fractionate bilirubin, if total bilirubin \geq 2xULN Obtain complete blood count with differential to assess eosinophilia Record the appearance or worsening of clinical symptoms of liver injury, or hypersensitivity, on the AE report form Record use of concomitant medications on the concomitant medications report form

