
MONITORING:
 
For bilirubin or INR criteria:
 
 Repeat liver chemistries (include ALT, AST, alkaline phosphatase, bilirubin) and perform liver event follow up assessments within 24 hrs Monitor subjects twice weekly until liver chemistries resolve, stabilize or return to within baseline A specialist or hepatology consultation is recommended 
For All other criteria:
 
 Repeat liver chemistries (include ALT, AST, alkaline phosphatase, bilirubin) and perform liver event follow up assessments within 24-72 hrs Monitor subjects weekly until liver chemistries resolve, stabilize or return to within baseline 	
including acetaminophen, herbal remedies, other over the counter medications.
 
 Record alcohol use on the liver event alcohol intake case report form 
For bilirubin or INR criteria:
 
 Anti-nuclear antibody, anti-smooth muscle antibody, Type 1 anti-liver kidney microsomal antibodies, and quantitative total immunoglobulin G (IgG or gamma globulins). Serum acetaminophen adduct High-performance liquid chromatography (HPLC) assay (quantifies potential acetaminophen contribution to liver injury in subjects with definite or likely acetaminophen use in the preceding week [James, 2009]). NOTE: not required in China Liver imaging (ultrasound, magnetic resonance, or computerised tomography) and /or liver biopsy to evaluate liver disease; complete Liver Imaging and/or Liver Biopsy CRF forms.
---	--

- Serum bilirubin fractionation should be performed if testing is available. If serum bilirubin fractionation is not immediately available, discontinue study treatment for that subject if ALT \geq 3xULN **and** bilirubin \geq 2xULN. Additionally, if serum bilirubin fractionation testing is unavailable, **record presence of detectable urinary bilirubin on dipstick**, indicating direct bilirubin elevations and suggesting liver injury.
- All events of ALT \geq 3xULN **and** bilirubin \geq 2xULN (>35% direct bilirubin) or ALT \geq 3xULN **and** international normalized ratio (INR) >1.5, if INR measured which may indicate severe liver injury (possible 'Hy's Law'), **must be reported as an SAE (excluding studies of hepatic impairment or cirrhosis)**; INR measurement is not required and the threshold value stated will not apply to subjects receiving anticoagulants

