#### **Parts A/B**

Subjects who discontinue open-label mepolizumab/withdraw from study participation during Part A/B were expected to return to the clinic for an Early Withdrawal (EW) visit and to return any study materials approximately 4 weeks following their last dose of open-label mepolizumab. No additional follow-up is needed.

If a subject completes a Parts A/B Early Withdrawal Visit at a scheduled visit at which endpoint data were not scheduled to be collected, data will be slotted to the nearest adjacent visit within Part A/B where the endpoint data was scheduled to be collected according to the Time and Events schedule ([Appendix 2: Schedule of Activities](#)) unless data are already recorded at that visit.

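### Protocol Section 6.5 ends follow-up at the Part A/B early withdrawal visit without exception, which read literally contradicts the liver monitoring in Appendix 3 and the pregnancy follow-up in Section 13.5.1; the practical gap is narrow

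*Protocol*

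**What the plan says.** Protocol Section 6.5 lists criteria under which Part A or B subjects must "discontinue study participation if any of the following stopping criteria are met". Criterion 1 is a liver chemistry stopping event, with a reference to Appendix 2; criterion 2 is a positive pregnancy test. The section closes by asking every subject who leaves in Part A or B to attend an EW visit and return study "materials approximately 4 weeks following their last dose of open-label mepolizumab. No additional follow-up is needed". SAP Section 11.3.3 (Parts A/B) repeats it: the EW visit is expected "approximately 4 weeks following their last dose of open-label mepolizumab. No additional follow-up is needed".

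In the text available, Appendix 2 gives algorithm titles and the pointer "Liver Safety Required Actions and Follow up Assessments Section can be found in" Appendix 3. Appendix 3 sets out "Required Actions and Follow up Assessments following ANY Liver Stopping Event". For the bilirubin and INR criteria it asks for twice-weekly chemistries with the same end-points as for the rest. For all other criteria the instruction is "Monitor subjects weekly until liver chemistries resolve, stabilize or return to within baseline". It does not treat every such event as serious: the site must "Complete the liver event CRF and complete an SAE data collection tool if the event also meets the criteria for an" SAE.

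**The concern.** Section 6.5 sets a fixed end to follow-up, and Appendix 3 sets an end that depends on the chemistries. A subject whose ALT is still raised at the EW visit falls under both, and no visible text says which prevails. A site that takes Section 6.5 at its word could stop checking a subject who has just met a liver stopping criterion on active drug, since everyone in Parts A and B receives mepolizumab. What is at stake is that subject's safety and the completeness of the outcome record for a possible drug-related liver event.

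**Working it through.** No arithmetic in the plan bears on this point, so the check sets the texts side by side.

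1. **Scope of the Section 6.5 sentence.** It applies to all subjects who discontinue open-label mepolizumab or withdraw during Part A or B, so it includes exits under criterion 1. The EW visit falls 4 ± 1 weeks after the last dose (footnotes to Tables 5 to 7) and includes liver function tests.

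2. **Scope of Appendix 3.** It covers any liver stopping event, is not limited by study part, and has no time limit. It also lets the subject stay in the study for follow-up assessments. Section 6.6 allows that in Parts C and D, where only investigational product stops. Section 6.5 does not allow it in Parts A and B, where participation itself must end.

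3. **A second duty meets the same sentence.** Section 13.5.1 requires a pregnancy to be followed to its outcome and cites Section 6.5 among the withdrawal routes. The literal sentence contradicts this too. That is also good evidence that the literal sense was not intended. Section 6.7.2, for Parts C and D, uses narrower wording: it dispenses only with a further safety follow-up visit.

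4. **What Section 8.4.1.3 catches.** It follows all SAEs, and non-serious AEs of special interest tied to the Table 3 risks, until resolution or stabilisation. Appendix 3 makes bilirubin and INR events reportable as SAEs, so those are covered. Neither Table 3 nor the special-interest list in SAP Section 11.6.4 contains a hepatic event, so a non-serious ALT-only event is not covered.

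5. **Which stopping criteria can produce such an event.** Thresholds by row of the Appendix 3 table:
   - ALT absolute 1, ALT increase 2, bilirubin 1, INR 1, cannot monitor 2, symptomatic 1. Total: 6 rows, 1 + 2 + 1 + 1 + 2 + 1 = 8 thresholds.
   - Bilirubin and INR are mandatory SAEs: 6 − 2 = 4 rows and 8 − 2 = 6 thresholds remain.
   - A symptomatic event attributed to hypersensitivity could count as a Table 3 systemic reaction. Leaving that row out: 3 rows, 5 thresholds.
   - The cannot-monitor row is defined by weekly monitoring being impossible, so missed weekly checks there could not be blamed on Section 6.5. Leaving it out: 2 rows (ALT absolute and ALT increase), 5 − 2 = 3 thresholds.

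   This shows which criteria are exposed. It says nothing about how often they occur.

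6. **Whether an event can still be open at EW.** As an illustration, a Part A sample is drawn before dosing, mepolizumab is given the same day, and ALT returns at 3 to <5 times ULN. Appendix 3 allows treatment to continue with weekly checks, and persistence for 4 weeks (28 days) makes it a stopping event. EW is due 3 to 5 weeks (21 to 35 days) after that dose, so the stopping event and the EW visit can coincide with ALT still raised.

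**The case against.** The strongest reply is that there is no working conflict. Saying that follow-up is not needed does not forbid it. The sentence sits beside attending a visit and handing back materials, so it reads naturally as being about visits. Appendix 3 is the more specific rule, and Section 6.5 leads to it through Appendix 2. Other texts point the same way:
- Table 9, note 1 (Section 8.4.6) refers directly to Appendices 2 and 3 for actions and follow-up after a liver stopping event.
- Section 8.4.6 asks for clinically significant abnormal values to be repeated until normal or baseline and, failing that within a reasonable period, for the etiology to be identified and the sponsor notified.
- Section 13.4.5 obliges the investigator to arrange supplemental measurements that are indicated or that the sponsor requests.
- Section 13.4.2 refers to Appendix 2 for liver chemistry follow-up.
- Appendix 3 requires a report within 24 hours and a liver event form.
- SAP Listings 39, 42 and 43 cover Parts A/B.

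Most of this stands, and it is why the gap is narrow. It does not remove the contradiction, because none of these texts qualifies the Section 6.5 sentence. Section 8.4.6 sets no interval and depends on the investigator's judgement of clinical significance. The Section 13.4.2 pointer sits with the bilirubin and INR events, which are SAEs already. A listing can show only chemistries that were taken. The SAP sentence is immaterial to conduct: it restates the protocol, and sites do not manage liver events from a SAP.

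One limit remains. The Appendix 2 flow charts are missing from the text available, so whether they address this case cannot be checked.

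**Conclusion.** The Section 6.5 sentence is wrong as written, and severity is minor. It contradicts Appendix 3 and Section 13.5.1 on a literal reading, although routine visits were probably what was meant. The exposed case is mainly a non-serious, ALT-only stopping event in Part A or B that is unresolved at EW. The conclusion assumes that the unseen Appendix 2 charts do not settle precedence.

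A reader might infer three stronger things that the documents do not support:
- That liver monitoring stops for every Part A/B liver event. Bilirubin and INR events are SAEs and are followed under Section 8.4.1.3, and the other texts lead sites to continue with the rest.
- That a number of lost checks can be stated. The documents give neither the frequency of such events nor how long they stay open, and any count would have to assume the literal reading.
- That the trial's comparison is at risk. These subjects leave before randomisation, so the Part C population and the primary analysis are untouched.

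**What to change.** In Protocol Section 6.5, replace the closing sentence with: *No additional routine study visits are needed; unless consent is withdrawn, event follow-up continues as required by Sections 8.4.1.3 and 8.4.6, Appendix 3 (liver events) and Appendix 5 (pregnancy).* In criterion 1, cite Appendix 3 next to Appendix 2. Nothing further is needed on treatment restart or run-in failure status, which Sections 6.4 and 6.5 already cover.

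Align the sentence in SAP Section 11.3.3, citing these as protocol sections, for consistency only.

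The cost is one replaced sentence and one cross-reference in the protocol, and one replaced sentence in the SAP. No assessment is added, because each is already required by the sections cited.

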6.6. Discontinuation of Investigational Product (IP) during Part C or Part D

Subjects in study Part C or D who have permanently discontinued double-blind or open-label IP are NOT required to withdraw from the study. Subjects have the right to permanently discontinue IP before the end of the study. A subject may also be asked to discontinue IP at the investigator's discretion or because the subject met the protocol defined IP discontinuation criteria detailed below. Subjects who discontinue IP, but remain in the study will be treated per local standard of care, according to the judgment of the investigator.

Subjects in Parts C or D of the study **MUST** discontinue IP permanently if either 1, 2 or 3 of the following stopping criteria are met:

1. **Liver Chemistry:** Meets any of the protocol-defined liver chemistry stopping criteria (see [Appendix 2](#)).

Liver chemistry stopping and increased monitoring criteria have been designed to assure subject safety and evaluate liver event etiology (in alignment with the FDA premarketing clinical liver safety guidance).

<http://www.fda.gov/downloads/Drugs/GuidanceComplianceRegulatoryInformation/Guidances/UCM174090.pdf>

If the liver chemistry stopping criteria are met by any subject participating in this study, treatment restart or re-challenge is not permitted.

2. **Pregnancy:** Positive pregnancy test

3. **ECG:** Discontinuation is required if any of the following ECG criteria are met during the study:
- QTcF > 500 msec or uncorrected QT > 600 msec
 - Change from Visit B1 baseline: QTcF > 60 msec

For patients with underlying **bundle branch block**, follow the discontinuation criteria listed below:

Visit B1 Baseline QTc with Bundle Branch Block	Discontinuation QTc with Bundle Branch Block
< 450 msec	> 500 msec
450 – 480 msec	≥ 530 msec [Note: QTc(F) > 500 msec for Korean subjects]

Details on performing ECG assessments can be found in Section 8.4.5.

Subjects in Part C who meet IP discontinuation criteria 1, 2 or 3 will not be eligible to switch to open-label Part D.

Subjects who have permanently discontinued IP and have not withdrawn consent may continue in the study. Subjects wishing to remain in the study will complete an IP Discontinuation Visit (approximately 4 weeks after the last dose and may be at the same time as a scheduled visit) and continue to attend the clinic visits at the protocol designated time intervals and complete eDiary daily and weekly entries for important efficacy and safety assessments. However, if this is not possible then the investigator will encourage the subject to participate in as much of the study as they are willing (or able) to. Guidance is provided in the study reference manual (SRM) and can be used by the investigator to discuss and agree the appropriate level of ongoing study participation with subjects, after they have discontinued IP.

If the subject is unable to visit the clinic to complete any study assessments which require physical presence of the subject, visits will occur by telephone contact to review the following:

- Exacerbations
- Adverse Event (AE)/Serious Adverse Events (SAEs)
- Concomitant medications

Subjects discontinuing IP, but remaining in the study should continue to record on their paper diary any medical problems experienced during the study, and any medication taken for those medical problems.

6.6.1. IP Discontinuation Visit Assessments

The Investigator must make every effort to have the subject return to the clinic approximately 4 weeks after the subject permanently discontinues IP in order to complete the IP Discontinuation Visit. Evaluations and procedures as outlined in the Time and Events Tables ([Table 5](#), [Table 6](#), [Table 7](#) and [Table 8](#)) should be completed and recorded in the eCRF as required.

6.6.2. Reasons for Discontinuation of IP

The primary reason for permanent discontinuation of IP will be recorded in the eCRF on the IP discontinuation form. Specific regard should be given to distinguishing permanent discontinuation of IP due to an adverse event from other reasons for permanent discontinuation of IP.

6.7. Study Withdrawal During Part C or Part D

6.7.1. Study Withdrawal Criteria

For this study there are no pre-determined protocol specific study withdrawal criteria (see Protocol Defined IP Discontinuation Criteria, Section [6.6](#)).

6.7.2. Study Withdrawal Assessments

If a subject is withdrawn from the study for any reason, including but not limited to the Protocol Defined IP Discontinuation Criteria (Section [6.6](#)), the Investigator must make every effort to have the subject to return to the clinic for an EW Visit approximately 4 weeks following the last dose to perform EW Visit assessments and to return all study-related materials. Assessments are described in the Time and Events Tables ([Table 5](#), [Table 6](#), [Table 7](#) and [Table 8](#)).

Subjects who have previously discontinued IP and have already completed their IP Discontinuation Visit (approximately 4 weeks following the last dose) but then decide at a later date that they no longer wish to participate in the study, will be asked to return to the clinic to complete an EW Visit (approximately 4±1 weeks) to complete any EW assessments, as agreed by the subject and investigator, and to return any remaining study materials. No additional safety follow-up visit is required.

6.7.3. Reasons for Withdrawal

The primary reason for study withdrawal will be recorded in the eCRF. Specific regard should be given to distinguishing withdrawal due to an adverse event from other reasons for withdrawal.

